4. PATIENT ENROLLMENT AND EVALUATION

- 4.1. Study participants will be recruited through the following means:
 - (1) The University of Michigan Rogel Cancer Center physicians, advanced practice providers, and nurse coordinators.
 - (2) The University of Michigan health system's electronic health record (EHR) is based on the Epic software (MiChart), which allows researchers, with IRB approval, to contact (via email, flyers, phone calls, or in-person) individuals who meet specific criteria and may be eligible to participate in the study. For example, with IRB-approval, Drs. [name], [name], and [name] and their Research Staff can access the daily clinic schedules, which will enable them to identify potential participants and meet them in-person during a corresponding patient encounter.
 - (3) With IRB-approval, we will distribute flyers in the outpatient clinics for our three cancer populations to inform potential individuals about the study. We will also distribute emails to potential study participants via the University of Michigan's UMHealthResearch (<https://umhealthresearch.org>) service.
 - (4) The Michigan Institute for Clinical and Health Research (MICHR), supported by the NIH Clinical and Translational Science Award Program, will assist our team with developing and reviewing recruitment materials, and identifying obstacles that may affect participant recruitment and retention.
- 4.2. *Randomization*: Once the patient is deemed eligible and has provided written informed consent, the Research Coordinator will confirm eligibility. The study statistician, [name], will create a randomization list before the study begins enrollment using the statistical package R. [name] will then forward the list to the Data Manager, who will be responsible for enrolling patients and assigning them to the correct study arm.
- 4.3. *Pre-Intervention Evaluation*: PROMIS Patient-Reported Outcomes (PROs) – Well-being or HRQOL assessments will be obtained at baseline, pre-intervention. The surveys will be completed directly through the SYNC app on mobile phones. Based on prior work, our Study Team has experience administering PROMIS PROs on mobile devices.
- 4.4. *Post-Intervention Evaluation*: PROMIS Patient-Reported Outcomes (PROs) – Well-being or HRQOL assessments will be completed at 12 weeks, post-intervention. This survey must be completed within two weeks after the 12-week intervention period. The surveys will be obtained directly through the SYNC app on mobile phones. Based on prior work, our Study Team has experience administering PROMIS PROs on mobile devices.
- 4.5. *Participant Withdrawal*: At any time, a participant may request that her or his data no longer be collected. The participant may make this request to the Research Coordinator or to any member of the Study Team. A note will be made in the patient chart documenting the reason the patient withdrew from the study. Participants may also be removed for the following reasons: development of disease recurrence or progression, in the event that the IRB or sponsor decides to close the study, or if the treating physician thinks it is no longer in the best interest of the patient.
- 4.6. *Study Regulations*: The trial will be performed in accordance with all applicable regulatory requirements and laws.
- 4.7. *Risks*.

4.7.1. Wearable Sensor Device: Patient Subjects who agree to wear the device(s) for data collection may experience mild skin irritation, which will be monitored by the care team. The subject can decline to wear the device(s) or request to try a different device(s) that may be more comfortable. Subjects who decline to wear the wearable device will be replaced and not included in the statistical analysis. All subjects will be instructed to remove the device before any scans or radiation therapy.

4.7.2. Confidentiality: There is a possible risk of loss of confidentiality. However, every effort will be made to keep your medical information confidential. We will code data by assigning a number to each individual patient and then store the data by that number. No mention of patient subject identities is made in analyses of the data or in any publications, which result from such research.

4.8. **Adverse Event Reporting Requirements.**
Adverse events related to this intervention are not expected, as the focus of this intervention (if randomized to the intervention group) is on lighting and minimal-risk behavioral interventions. However, any adverse events resulting from research procedures will be reported to IRBMED per institutional guidelines. In the event an AE does occur, the PI will determine the attribution/relatedness of each AE. Expected side effects from anti-hormonal therapies, anti-HER2 therapy, GVHD will not be reported for this trial.

4.9. ***Participant Data Security and Compliance***. All identifiable information about the patient will be stored on a secure, password-protected core image laptop computer in [name] [name]'s Laboratory (MPB) following rules for secure data storage (e.g., M+Box or Dropbox). Research devices will not interface with MiChart. All study personnel will be HIPAA and PEERRS certified. All study information will be stored in password-protected encrypted files and identified by case number. The technologies proposed in this proposal have all been carefully reviewed, and approved by the governing bodies at Michigan Medicine. All regulatory and security requirements have been met and have been fully documented in accordance with the policies and best practices that govern the use of technology for patient care and research at Michigan Medicine. The MiChart web services were built and are supported by HITS, and their use for this project has been approved by HITS. All standard procedures and protocols for security and data integrity that apply to this project are being followed. All PHI will be stored in the HITS Oracle Database.

4.10. ***Data Safety Monitoring Plan***. This study will be monitored in accordance with the NCI approved University of Michigan Rogel Cancer Center Data and Safety Monitoring Plan. The study team will meet every six months or more frequently depending on the activity of the protocol. The discussion will include matters related to the safety of study participants (SAE/UaP reporting), validity and integrity of the data, enrollment rate relative to expectations, characteristics of participants, retention of participants, adherence to the protocol (potential or real protocol deviations) and data completeness. At these regular meetings, the protocol specific Data and Safety Monitoring Report form will be completed and signed by the Principal Investigator or by one of the co-investigators. Data and Safety Monitoring Reports will be submitted to the University of Michigan Rogel Cancer Center Data and Safety Monitoring Committee (DSMC) every six months for independent review.

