1.4.2. Exclusion Criteria

- 1.4.2.1. The patient cannot be undergoing chemotherapy at the time of enrollment unless it is post-transplant maintenance chemotherapy. Patients undergoing post-transplant maintenance chemotherapy are permitted to enroll.
- 1.4.2.2. The patient must have no evidence of disease progression or recurrence. Specifically, for the prostate cancer population, the patient must have no evidence of disease progression on their current ADT regimen at the time of enrollment.
- 1.4.2.3. The patient must not be a night shift worker, where night shift is defined as working a significant number of hours (i.e. more than half) between the hours of 11PM and 6AM on a regular basis.

1.5. *Intervention Plan*

- 1.5.1. Participants will be consented, enrolled, and randomized remotely with a Research Coordinator prior to beginning the trial. A review of inclusion/exclusion criteria will be conducted to determine the patient's eligibility for enrollment. Study procedures will be reviewed with the patient, and documentation of informed consent will be obtained. After signing the informed consent form (ICF) either in person or electronically using SignNow or other process approved by the University of Michigan IRBMED, patients will be assigned a unique study ID number in sequential order. Those who are found to be ineligible will be replaced.
- 1.5.2. After providing informed consent, the participant will be provided, in the clinic or via mail, a wearable device and a pair of glasses, which will be either blue-blocking (intervention group) or clear (control group). Both of these are described in detail in **Appendix A**. When both are in the participant's possession, the study coordinator will schedule a second meeting with the participant to onboard them to the specifics of the study.

- 1.5.3. The study coordinator will walk the participant through setting up the app and entering their Research ID number. They will ensure that the participant is able to connect to the wearable device via their phone and will explain to the subject that they should not wear the blue-blocking glasses while driving or if their vision will be impaired by them in a way that challenges their mobility.

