5. STATISTICAL CONSIDERATIONS

- 5.1. *Study Design.* The clinical trial is a two-arm randomized controlled trial. After completion of the intervention, data analysis will be conducted according to the statistical analysis plan outlined below. Descriptive statistics will be performed prior to conducting the statistical analyses. An intention-to-treat (ITT) analysis of the results will be based on the initial assignment of the randomized participants. With the ITT approach, participants will be analyzed according to the treatment assignment, even if the participant drops out of the study. The ITT approach minimizes biased comparisons among the treatment arms. Missing data will be imputed using the last collected data from the subject prior to dropout.
- 5.2. *Accrual.* It is estimated that 18-months will be necessary to enroll the targeted sample size. Accrual will be reported by race, ethnicity, gender, and age.
- 5.3. *Study Duration.* Survey results and wearable data will be actively collected from participants over the course of 12 weeks. At the conclusion of the 12 weeks, passive collection of wearable data through the app will continue for up to one year for each participant who opts-in to continue using the app. Medical records may be accessed for up to five years after the conclusion of the 12-week collection period.
- 5.4. *Randomization.* Blocked randomization will be used to limit bias and achieve an equal distribution of participants to the intervention and control arms of the study (69 randomized, 69; with 23 from each cancer population in each arm). This approach will recruit participants in small blocks to ensure that half of the participants within each block will be allocated to the treatment and the other half to the control. The size of the blocks will be permuted to limit selection bias, and within each block, the order of patients will be random. The study statistician will create a randomization list before the study begins enrollment using the statistical package R. This list will be used by the study group in assigning patients to the correct study arm.
- 5.5. *Blinding.* Study arm assignments cannot be blinded to the investigators or the rest of the study team because it will be known whether participants have SYNC on their mobile device or not (due to technical purposes).

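### Section 4.2 gives the pre-made randomisation list to the Data Manager, a role that also enrols, and no passage restricts access to the list or releases assignments one at a time

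*Combined protocol and SAP*

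**What the plan says.** Section 4.2 (Randomization) starts with eligibility and consent: "Once the patient is deemed eligible and has provided written informed consent, the Research Coordinator will confirm eligibility". The statistician, having made the list in advance, "will then forward the list to the Data Manager, who will be responsible for enrolling patients and assigning them to the correct study arm".

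Section 5.4 (Randomization) repeats the timing, "The study statistician will create a randomization list before the study begins enrollment using the statistical package R", and then describes use of the list more loosely: "This list will be used by the study group in assigning patients to the correct study arm". The one measure it directs at selection bias is the varying block size: "The size of the blocks will be permuted to limit selection bias". Order within a block is random.

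Study Design 1.5.1 (Intervention Plan) describes the same steps with another role: "Participants will be consented, enrolled, and randomized remotely with a Research Coordinator prior to beginning the trial". It lists the criteria review first, then consent, and after consent "patients will be assigned a unique study ID number in sequential order". Under 1.5.2, also after consent, "the participant will be provided, in the clinic or via mail, a wearable device and a pair of glasses"; the type of glasses depends on the arm.

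Section 5.5 says that the study team is not blinded to arm. No passage mentions allocation concealment, sealed envelopes, central or web-based release, disclosure of one assignment at a time, or any limit on who may see the list.

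**The concern.** Randomisation protects the comparison only if whoever decides when, or whether, a patient is entered cannot know the next arm. Section 4.2 puts the list and the duty to enrol in one role, and the other two sections do not separate them again. A person with both could delay, hasten or decline an entry according to the arm that comes next. The arms could then differ in prognosis from the start, and the test would attribute that difference to the app.

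The outcomes are self-reported and the team is unblinded, so the trial depends heavily on sound allocation. Concealment also cannot be restored once patients have been entered.

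**Working it through.** **1. The three sections side by side**

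| Step | 1.5.1 | 4.2 | 5.4 |
|---|---|---|---|
| Confirms eligibility | Criteria review; role not separately named | Research Coordinator | – |
| Enrols | With Research Coordinator | Data Manager | – |
| Assigns arm | Randomised with Research Coordinator | Data Manager | Study group |
| Holds or uses the list | – | Data Manager | Study group |

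The sections disagree on who enrols and who assigns. None of them keeps any enrolling role away from the list.

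**2. Does varying the block size cover the gap?** It makes the next arm harder to guess from past arms. A list holder does not guess: the chance g of knowing the next arm is 1 whatever the block sizes.

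**3. The plan's own figure.** For 0.5 SD, two-sided 0.05 and power 0.80 (5.7), the t-test needs 63.77, so 64 per arm, with power 0.801. Dropout: 64/0.93 = 68.8, so 69. Both reproduce, and concealment changes neither.

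**4. What a bias would do (bias sizes assumed).** With no true effect and a bias b in SD units, the t statistic has 2 × 64 − 2 = 126 df and noncentrality b × √(64/2) = 5.657b.

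| Assumed b (SD) | Noncentrality | Type I error |
|---|---|---|
| 0 | 0 | 5.0% |
| 0.025 | 0.141 | 5.2% |
| 0.05 | 0.283 | 5.9% |
| 0.10 | 0.566 | 8.7% |
| 0.20 | 1.131 | 20.2% |

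Read the other way, 6% needs b = 0.0525 and 10% needs b = 0.116. To express this in patients, assume b = share steered × 2 × shift × (2g − 1). With g = 1 and a shift of 0.5 SD per steered patient, b equals the share steered: 0.0525 × 128 = 6.7 patients, or 0.1162 × 128 = 14.9. With a shift of 0.25 SD the counts double, to 13.4 and 29.7.

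**5. What concealment would leave.** Without the list, someone who knows past arms (5.5) can guess the arm that is behind. The documents give no block sizes, so I simulated the sets {2,4}, {2,4,6}, {4,6} and {4,6,8}, as one list of 138 or three lists of 46. The share of the bias that remains is 2g − 1.

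- *Steering at random slots, coin toss when tied:* g = 68–72%. From the unrounded extremes, 2 × 0.677 − 1 = 0.354 and 2 × 0.722 − 1 = 0.444, so 35–44% remains.
- *Steering only when past arms are unequal:* such slots are 55–64% of the total, about 76–88 of 138. There g = 78–90%, and 2 × 0.78 − 1 = 0.56 to 2 × 0.90 − 1 = 0.80, so 56–80% remains.

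| Bias with the list | Type I error with the list | Concealed, random slots | Concealed, unequal slots only |
|---|---|---|---|
| 0.05 SD | 5.9% | 5.1–5.2% | 5.3–5.6% |
| 0.10 SD | 8.7% | 5.5–5.7% | 6.1–7.3% |
| 0.20 SD | 20.2% | 6.8–7.9% | 9.6–14.6% |

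**The case against.** The best defence is that the one role shown to have the list is not shown to meet patients. Recruitment (4.1) is by clinicians, research staff, flyers and email. The Research Coordinator works with the patient and confirms eligibility. In 4.2, consent and confirmed eligibility come first, so the Data Manager's enrolling may mean no more than registering a patient whom someone else has cleared. On that reading, steering would require disclosure to recruiters, which no passage describes. The study group in 5.4 may simply restate 4.2. That the whole list is forwarded is itself an inference, though a fair one, because the list is finished before enrolment and no staged release is described.

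Much of this stands, and it limits the point. It does not answer it: 4.2 still makes the list holder responsible for enrolling, and no passage keeps the coordinator or recruiters from the list.

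A reader might infer more than the documents support in three ways:

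- *That the list holder could select on fatigue, and the analysis would not correct it.* A fatigue rating does exist at screening (1.4.1.6), but no passage gives it to the Data Manager. The covariates in 5.12 are examples, so baseline fatigue is not excluded, and the t-test there is worded for Global Health scores. The documents give no correlation between the screening item and any endpoint.
- *That the arm is fixed by the study ID before eligibility is settled.* The Synopsis says that the research ID sets the app version, but no passage says that the sequential study ID is that ID. Study Design 1.5.1 places both the criteria review and consent before the ID.
- *That concealment would bring the error rate back to 5%.* Step 5 of the working shows that it would not if someone guesses from past arms.

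**Conclusion.** The point holds as a stated rule that should be changed and as three sections that should be reconciled. A role named as enrolling holds the upcoming assignments, access to the list is not limited, and the stated safeguard does not work against a list holder. Foreknowledge is shown for the Data Manager only. The documents do not show that patient-facing staff see the list or that any steering took place.

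The size of any bias cannot be derived. The type I error figures are illustrations that rest on assumed biases, and below about 0.05 SD the effect is small. The benefit of concealment also depends on assumed block sets and on how a person would steer: about 35–44% or 56–80% of the modelled bias would remain. The case for change therefore rests on the rule and on how little it costs to correct. This is a cheap improvement, not a demonstrated bias.

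**What to change.** 1. Reconcile 1.5.1, 4.2 and 5.4 on who enrols and who assigns.
2. Keep the list with the statistician or in an electronic randomisation module, with no access for anyone who recruits, consents, confirms eligibility or enrols. Delete its use by the study group from 5.4.
3. Release each assignment singly, after consent, confirmed eligibility and irreversible registration, and before glasses are sent.
4. Do not disclose block sizes to enrolling staff.

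If a concealed process is already used in practice, writing it down is enough.

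Cost: setting up a module, or manual release by the statistician. With 138 patients over 18 months (5.2), 138/18 = 7.7, so about 8 releases a month, plus any replacements. Where glasses are handed over in clinic (1.5.2), manual release may cause a short wait, which a module would avoid. No extra patients are needed, and the sample size and analysis do not change.

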- 5.6. *Primary Endpoint.* The primary objective of the study is to test the effects of SYNC in a randomized controlled clinical trial design. Patients will be randomly assigned to the treatment arm or the control arm. The primary objective is to quantify the effects of the light interventions delivered by SYNC on patient fatigue.
- 5.7. *Sample Size Considerations.* We will enroll 138 cancer patients, with half in the intervention arm and half in the control arm. Our primary endpoint is the PROMIS 4-item Fatigue Short Form. The age- and sex-adjusted norm for the Fatigue scale is 50 points, with a standard deviation of 10 points. These statistics have been shown to be largely generalizable to the cancer patient population (mean: 52, standard deviation 7.6). Our study will have power of 0.80, assuming a two-sided Type I error rate of 0.05, to detect an effect size of half the standard deviation between the intervention and control arms if 64 cancer patients are enrolled in each of the control and intervention groups. A mean difference of one-half a standard deviation is clinically meaningful and is considered a medium effect size for clinical trials. During the primary analysis, we will adjust for the fact

that there are three cancer populations in our data and will look for a well-defined effect that is marginal within each population. We will accrue a total of 69 patients in each arm to account for attrition of data, assuming a 7% dropout rate from the trial.

5.8. PROMIS® measures use Item Response Theory (IRT), a family of statistical models that link individual questions to a presumed underlying trait or concept of global health represented by all items in the scale. PROMIS® instruments are scored using item-level calibrations. The most accurate way to score a PROMIS® instrument is to use the Health Measures Scoring Service, which our Study Team has experience with. This method of scoring uses “response pattern scoring,” which uses responses to each item for each participant. Response pattern scoring is especially useful when there is missing data (i.e., a respondent skipped an item), or different groups of participants responded to different items).

There are four key features of the score for PROMIS® Fatigue:

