1. Reliability: The degree to which a measure is free of error. It can be estimated by the internal consistency of the responses to the measure, or by correlating total scores on the measure from two time points when there has been no true change in what is being measured (for z-scores, reliability = $1 - SE^2$).
2. Precision: The consistency of the estimated score (reciprocal of error variance).
3. Information: The precision of an item or multiple items at different levels of the underlying continuum (for z-scores, information = $1/SE^2$).
4. Standard Error (SE): The possible range of the actual final score based upon the scaled T-score. For example, with a T-score of 52 and a SE of 2, the 95% confidence interval around the actual final score ranges from 48.1 to 55.9 ($T\text{-score} \pm (1.96 \times SE) = 52 \pm (1.96 \times 2) = 48.1 \text{ to } 55.9$)

The final score is represented by the T-score, a standardized score with a mean of 50 and a standard deviation of 10 points.

5.9. *Interim Analysis*. There will be no interim analyses for efficacy or futility for this trial.

5.10. *Patient Characteristics*. Patient characteristics will be summarized for all participants. Patient characteristics to be examined may include: age, gender, race/ethnicity, treatment and pathology information (including dates), and clinical outcomes; e.g. survival, relapse, and toxicities.

5.11. *Analysis Populations and General Analysis Guidelines*.

5.11.1. Primary Analysis Population. All participants enrolled, consented, and completing at least the baseline outcome measures will be included in the primary analysis population. Analyses for the primary and secondary endpoints will use the primary analysis population: The primary analysis will occur once all patients have been followed for the duration of the 12-week trial, data adjudication completed, and data are locked.

5.11.2. General Analysis Guidelines. Primary analyses for the primary, secondary, and exploratory endpoints will use the primary analysis population. Analyses of each endpoint in each population will follow the

analysis plans, as described below. We expect minimal missing data (<5%) for the primary endpoint and secondary endpoints based on past experience with mobile app studies.

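### Participants may be removed at recurrence or progression with no later fatigue collection specified, and their last pre-removal score is then carried forward in the intention-to-treat analysis

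*Combined protocol and SAP*

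**What the plan says.** Section 4.5 (Participant Withdrawal) first gives the participant the right to ask that data collection stop. The same paragraph then provides that a participant may be taken off the study, with "development of disease recurrence or progression" as the first reason listed. It adds closure of the study and the treating physician's view of the patient's interest as further grounds. The wording is permissive, and no criteria say when removal applies. Nothing in 4.5 or elsewhere says whether surveys continue after a removal that the participant did not request.

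Section 5.1 promises intention-to-treat: "participants will be analyzed according to the treatment assignment, even if the participant drops out of the study". It then states: "Missing data will be imputed using the last collected data from the subject prior to dropout". Under section 5.11.1, anyone "completing at least the baseline outcome measures will be included in the primary analysis population". A removed participant therefore stays in the analysis with a pre-removal score.

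The exclusion criteria (1.4.2) require of every entrant: "The patient must have no evidence of disease progression or recurrence". Section 5.5 says that investigators and study team cannot be blinded. No estimand, repeated-measures model or sensitivity analysis is given for removals of this kind.

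**The concern.** Stopping the intervention and stopping outcome measurement are two decisions. Section 4.5 lists investigator- and physician-led removal beside a request to end data collection and does not separate them. An intention-to-treat comparison at week 12 needs the week-12 outcome whether or not the participant still follows the app.

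Everyone enters free of known progression, so the carried score dates from before progression was recognised. If fatigue then rises, the analysis uses too favourable a value for that patient. The missingness would be related to the outcome, and no imputation method can recover scores that were not collected. If one arm loses more patients this way, the bias favours that arm.

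**Working it through.** **The plan's own figures (section 5.7).** Inputs: effect 0.5 SD; "Our study will have power of 0.80", "assuming a two-sided Type I error rate of 0.05"; 1:1 allocation; 7% dropout. A two-sample t-test needs 63.8, so 64 per arm, with power 0.801 at 64. Allowing for dropout, 64 / (1 − 0.07) = 68.8, so 69 per arm. Both figures reproduce. In points, the target is 0.5 × 10 = 5.0 with the norm SD, or 0.5 × 7.6 = 3.8 with the cancer-population SD.

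**Formula.** Let p_I and p_C be the shares removed at progression in the intervention and control arms. Let D be the worsening between the last collected score and week 12, taken as equal in the two arms. Higher scores mean more fatigue.
- Carrying forward understates each arm's mean by p × D.
- The error in the difference (intervention minus control) is −(p_I − p_C) × D.

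**Inputs that the documents do not give.** No progression rate and no fatigue change at progression are stated. D = 5 to 10 points and all removal shares below are assumptions.

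**Balanced removal, 2% to 7% in each arm.** Each mean is understated by 0.02 × 5 = 0.1 to 0.07 × 10 = 0.7 points. The error in the difference is zero.

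**Excess of 2 to 4 removals out of 69 in one arm, D = 10.**
- 2/69 × 10 = 0.29 points: 0.29/5.0 = 6% or 0.29/3.8 = 8% of the target.
- 4/69 × 10 = 0.58 points: 0.58/5.0 = 12% or 0.58/3.8 = 15% of the target.

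**Percentage scenarios, with type I error of the t-test at 69 per arm, a true effect of zero and the SD unchanged.**

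| Removed (one arm vs other) | D | Shift (points) | Share of target, SD 10 / SD 7.6 | Type I error, SD 10 / SD 7.6 |
|---|---|---|---|---|
| 7% vs 2% | 5 | 0.25 | 5% / 7% | 0.052 / 0.054 |
| 7% vs 2% | 10 | 0.50 | 10% / 13% | 0.060 / 0.067 |
| 10% vs 4% | 5 | 0.30 | 6% / 8% | 0.054 / 0.056 |
| 10% vs 4% | 10 | 0.60 | 12% / 16% | 0.064 / 0.075 |

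**Plausibility.** Planned dropout from all causes is 0.07 × 69 = 4.8, about 5 per arm. Section 5.11.2 expects under 5% missing data, or under 0.05 × 69 = 3.5 per arm. An excess of 4 is therefore near the upper end, and the 10% vs 4% rows exceed the plan's own dropout assumption in one arm.

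**Sample size after the fix.** It stays at 69 per arm. With all 69 observed, power at 0.5 SD is 0.830. With 7% still lost, about 69 × 0.93 = 64 remain and power is 0.80.

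**The case against.** A reader might infer from 4.5 and 5.1 that patients are removed automatically at progression, that their surveys then stop, and that the result is biased by construction. The documents do not support that reading:
- Removal is allowed, not required. Section 4.5 ties the end of data collection only to the participant's own request and is otherwise silent.
- No passage says that fatigue worsens at progression.
- Fatigue is measured weekly, so with good completion the carried score would be about a week old at removal and may already show some decline.
- Entry is progression-free, the breast cancer patients are non-metastatic, follow-up is 12 weeks and randomization is blocked. Few removals are likely, and nothing suggests that the app or glasses affect progression. With balance, the difference is not biased.
- Section 5.5 unblinds the study team. It does not establish that the treating physician named in 4.5 knows the arm.

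Most of this stands, and it limits the size of the problem. It does not close the gap. A carried score about a week old at removal can still be many weeks old by week 12. The other PROMIS scales are collected only on the first and last day, so for them the last collected value would be the baseline. Clinicians recruit from their own clinics (section 4.1), so some treating physicians may know the arm. Removal has no stated criteria, so chance or discretionary imbalance cannot be excluded.

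Two practical objections also stand and shape the fix. Surveys are delivered inside the same app as the recommendations (1.5.5, Appendix B), so wording alone is not enough. Surveying by default would also sit badly with removal in the patient's interest, so continued surveys should be offered rather than imposed.

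**Conclusion.** The point holds in limited form. Followed as written, the plan can put a pre-event score in place of the week-12 outcome for participants removed at recurrence or progression or by the physician, in an analysis described as intention-to-treat.

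The likely effect is small. It is zero on the arm difference if removal and worsening are balanced. It is about 0.3 to 0.6 points, 6% to 15% of the 3.8 to 5 point target, under an assumed excess of 2 to 4 of 69 removals at 10 points each. Those assumptions, and the inference that fatigue worsens after progression, come from outside the documents. This is an inexpensive improvement to make, not a defect that threatens the trial's conclusion. Whether a participant should be removed at progression is a clinical matter and is not judged here.

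**What to change.** In section 4.5, separate stopping the intervention from stopping outcome collection:
- Participants removed for recurrence or progression, or by the treating physician, continue to be offered the weekly PROMIS Fatigue form and the exit survey to week 12, if they agree and have not asked for data collection to stop.
- In section 5.1, state that scores observed after removal are used in place of carried-forward values.
- Report removals and their reasons by arm.

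Whether and when a participant stops the intervention is unchanged, and so is the sample size. The change does not settle how scores that remain missing for other reasons are handled. Section 5.12 names Global Health rather than fatigue in the primary analysis, so the variable to which the rule applies also needs to be made consistent.

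Cost: protocol and consent wording; a survey-only app mode or a separate survey link, with loaner phones kept until week 12; and a small survey burden for a few patients who may be unwell. Surveys are already remote and coordinators already follow up missing ones, so little else is needed.
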